8.3. Average Daily Dose

For each drug, average daily dose (mg/day), defined as the cumulative dose divided by number of days dosed, will be calculated. A single average value will be computed for each subject, overall and within each cycle, and then the descriptive statistics will be computed for each treatment group.

8.4. Treatment Compliance

For each drug, treatment compliance (%) will be calculated for each subject for each cycle of treatment and overall. The compliance is defined as the ratio of the average total daily dose (mg/day) to the average calculated daily dose (mg/day). Calculated daily dose is the prescribed daily dose (mg/m²) multiplied by the subject's BSA (m²). Average calculated daily dose is defined as the sum of each calculated daily dose divided by the number of days of scheduled dosing (eg, 7 days / cycle for azacitidine). Compliance for each drug will be summarized using descriptive statistics overall and by cycle.

8.5. Dose Intensity

For each cycle, dose intensity for a study drug is defined as the cumulative dose of the study drug in the cycle divided by the cycle length. The overall dose intensity for each study drug is defined as the cumulative dose divided by the total length of cycles in treatment duration. A single average value will be computed for each subject, overall and within each cycle, and then the descriptive statistics will be computed for each treatment group.

8.6. Relative Dose Intensity

Relative dose intensity is defined as the actual dose intensity divided by the planned dose intensity;

- For durvalumab, the planned dose intensity (mg/day) is 1500 mg / 28 days.

- For azacitidine, the planned dose intensity (mg/day) is $75 \text{ mg/m}^2 * 7$ multiplied by the subject's BSA (m^2) / 28 days.

Descriptive statistics of overall and by cycle relative dose intensity will be summarized. Additionally, the number and percentage of subjects will be summarized by category such as $\leq 85\%$ and $> 85\%$ for relative total dose intensity of azacitidine, durvalumab, the actual category can be data driven.

8.7. Dose Modification

Dose modifications are permitted in any cycle for appropriate management of AEs or hematological toxicity. Dose reductions are only allowed for azacitidine.

Dose reduction is defined as a nonzero dose administered after the Cycle 1 Day 1 (C1D1) dose which is at a lower dose level than the dose the subject received at the previous dosing day. Dose interruption occurs if the record of actual administered dose is zero except as required by the protocol. If an interruption happens at the start of cycle and causes the cycle to be postponed, it is also called dose delay. Consecutive zeros are counted as one interruption.

Dose reduction or dose interruption will be summarized separately for azacitidine. Summaries include number of subjects who had at least 1 dose reduction (or interruption), time to first dose reduction (or interruption), number of subjects who had at least 1 dose reduction (or interruption) due to AE and time to first dose reduction (or interruption) due to AE will be provided.

Dose interruption as well as infusion interruption will be summarized for durvalumab. Dose delays are summarized for durvalumab only. Number of subjects who had at least 1 interruption, time to the first interruption, number of subjects who had at least 1 interruption due to AE and time to first interruption due to AE will be summarized.

An infusion interruption refers to an interruption of an infusion that actually started.

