### 3.2.2. Treatment Phase

The study will be conducted in 2 stages. Eligible subjects will be randomized 1:1 to one of two treatment arms:

Treatment Arm A: Subcutaneous azacitidine (75 mg/m^2 for 7 days Q4W) in combination with IV durvalumab at a dose of 1500 mg on Day1 Q4W

or

Treatment Arm B: Subcutaneous azacitidine alone at the dose of 75 mg/m^2 for 7 days Q4W.

The randomization process will aim to balance prognostic factors between study arms. For both cohorts (MDS and AML) subjects will be randomized and stratified according to their cytogenetic risk:

- Intermediate risk versus poor risk for AML (see Appendix J),
- Very good, good and intermediate risk versus poor and very poor risk for MDS (see Appendix H, IPSS-R Cytogenetic Risk Groups).

The subject should begin treatment on the day of randomization via integrated response technology (IRT) whenever possible, but the dose may be delayed for up to 5 days if necessary for logistical reasons. Any delay greater than 5 days must be discussed with, and approved by, the sponsor's medical monitor and may result in the need to repeat screening.

On Day 1 of each 28-day treatment cycle, subjects will receive IV infusion of durvalumab prior to receiving the first dose of subcutaneous azacitidine. Azacitidine dosing should not begin until any immediate toxicities from durvalumab infusion have resolved.

Azacitidine dose and schedule may be adjusted as described in Section 7.2.2.1 for the management of unacceptable toxicity.

Interruption or delay of treatment with subcutaneous azacitidine for up to 42 days is permitted as outlined in Section 7.2.2.1 to enable recovery from investigational product (IP)-related toxicity. If there is a delay of more than 42 days (6 weeks) in the start of the next cycle, the sponsor's

medical monitor must be consulted. When the start of a new treatment cycle with subcutaneous azacitidine is delayed for any reason, the infusion of durvalumab will also be delayed (in subjects randomized to the combination treatment arm), such that durvalumab and azacitidine continue to be administered on Day 1 of each treatment cycle. Study treatment should be discontinued if there is a delay of more than 56 days (8 weeks) in the start of the next cycle unless, in the opinion of the Investigator and the sponsor's medical monitor, the subject is experiencing clinical benefit.

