#### **Subjects without reduced baseline blood counts (ie, $\text{WBC} \geq 3.0 \times 10^9/\text{L}$ and absolute neutrophil count [ANC] $\geq 1.5 \times 10^9/\text{L}$ and platelets $\geq 75.0 \times 10^9/\text{L}$ ) prior to first treatment**

If hematological toxicity is observed following subcutaneous azacitidine treatment, the next cycle of subcutaneous azacitidine therapy should be delayed until platelet count and ANC have recovered. If recovery is achieved within 14 days, no dose adjustment is necessary. However, if recovery has not been achieved within 14 days, the dose should be reduced according to Table 4. Following dose modifications, the cycle duration should return to 28 days. The reduced dose should be maintained during subsequent cycles that are given (unless toxicity develops). A flow diagram for the determination of subcutaneous azacitidine dose adjustment in subjects without reduced baseline blood counts is provided in Appendix N2.

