## **9.7. Safety Analysis**

All subjects in the safety population who receive at least one dose of any assigned IP, will be included in the safety analyses. Adverse events, vital sign measurements, physical exam findings, clinical laboratory data, ECG interpretations, pregnancy tests for FCBP, concomitant

medications and procedures will be tabulated and summarized by treatment arm, and cohort, as appropriate.

Adverse events will be coded using Medical Dictionary for Regulatory Activities (MedDRA). Adverse event listings will include the verbatim term and the MedDRA preferred term. Adverse events will be graded according to CTCAE Version 4.03 criteria ([Appendix G](#)).

The frequency of AEs will be tabulated by MedDRA SOC and PT. In the by-subject analysis, a subject having the same event more than once will be counted only once. Adverse events leading to discontinuation from treatment, events leading to dose reduction/interruption/delay, events classified as CTCAE Version 4.03 Grade 3 or higher, IP-related events, AESI, imAEs and serious AEs will be tabulated and listed separately. By-subject listings of all AEs, and AESIs, serious AEs, and their attributes will be provided.

Clinical laboratory results will be summarized descriptively and will include a display of change from baseline. Laboratory values outside of the normal ranges will be identified. Laboratory data will be graded according to CTCAE Version 4.03 criteria for select analytes unless otherwise specified. The frequencies of the worst severity grade observed during treatment will be displayed in cross-tabulations by screening status. Clinically significant hematologic and nonhematologic laboratory abnormalities that meet Grade 3 or Grade 4 criteria according to CTCAE Version 4.03 will be listed and summarized.

Vital signs and ECG data will be summarized by cross-tabulations presenting normal and abnormal values by number of subjects at pre-and post-IP initiation.

Graphical displays will be provided where useful in the interpretation of results.

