- TEAEs leading to dose interruption of azacitidine, durvalumab and azacitidine and/or durvalumab;
- TEAEs leading to infusion interruption of durvalumab.

As well as

- TEAEs by cycle of onset;
- Serious TEAEs by cycle of onset;
- TEAEs related to azacitidine, durvalumab and azacitidine and/or durvalumab, by cycle of onset;
- TEAEs of CTCAE grade 3 by cycle of onset
- TEAEs of CTCAE grade 4 by cycle of onset;
- TEAEs of CTCAE grade 3 or 4 by cycle of onset;
- TEAEs by maximum CTCAE grade;
- TEAEs related to azacitidine, durvalumab and azacitidine and/or durvalumab, by maximum CTCAE grade;
- Common ($\geq 10\%$) TEAEs;
- Common ($\geq 10\%$) TEAEs related to azacitidine, durvalumab and azacitidine and/or durvalumab;
- By age category: <65 , $65-74$, ≥ 75
- By gender

Unless otherwise stated, TEAEs will be presented by MedDRA SOC and PT. To facilitate clinical study report writing the following tables will be produced

- TEAEs by PTs
- TEAEs by SOCs
- TEAEs related to azacitidine, durvalumab and azacitidine and/or durvalumab by PTs
- TEAEs related to azacitidine, durvalumab and azacitidine and/or durvalumab by SOCs
- TEAEs of CTCAE Grade 3 or 4 by PTs, by Grade (3 and 4 separately) and combined (3 or 4 combined)

- TEAEs of CTCAE Grade 3 or 4 by SOCs, by Grade (3 and 4 separately) and combined (3 or 4 combined)
- TEAEs related to azacitidine, durvalumab and azacitidine and/or durvalumab of CTCAE Grade 3 or 4 by PTs, by Grade (3 and 4 separately) and combined (3 or 4 combined)
- TEAEs related to azacitidine, durvalumab and azacitidine and/or durvalumab of CTCAE Grade 3 or 4 by SOCs, by Grade (3 and 4 separately) and combined (3 or 4 combined)

All deaths, on treatment deaths, off treatment deaths and causes of death will be summarized. On treatment deaths are defined as deaths occurring within 90 days after the last dose of durvalumab or 28 days after last dose of azacitidine. Off treatment death are defined as deaths occurring after that period. These summaries will be based on the death eCRF page.

Individual subject listing of AEs will be presented. In addition, the following tabulated lists will be provided:

- Listing of SAE;
- Listing of TEAEs leading to permanent withdrawal of any study drug
- Listing of all TEAEs with outcome of death
- Listing of all subjects who died

Adverse events of special interests (AESI)

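### SAP 8.7 confines the dose-delay summary to durvalumab, so azacitidine cycle delay is not summarised separately in either arm and the arms cannot be compared directly on it

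*SAP*

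**What the plan says.** SAP 8.7 treats delay as a form of interruption: "If an interruption happens at the start of cycle and causes the cycle to be postponed, it is also called dose delay". Interruption is itself defined through the dosing record: "Dose interruption occurs if the record of actual administered dose is zero except as required by the protocol". The drugs are then handled differently. For azacitidine, "Dose reduction or dose interruption will be summarized separately for azacitidine", with subject counts and time to first event, overall and due to AE. For durvalumab, interruptions and infusion interruptions are summarised, and delays are added for that drug alone: "Dose delays are summarized for durvalumab only".

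Protocol 7.2.2.1 makes cycle delay the opening step for hematological toxicity. For subjects without reduced baseline counts, "the next cycle of subcutaneous azacitidine therapy should be delayed until platelet count and ANC have recovered", and the dose is reduced only if recovery takes longer than 14 days. Subjects with reduced baseline counts are also delayed, but only after a fall of more than 50% in ANC or platelets with no improvement in cell line differentiation.

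Protocol 3.2.2 ties the two drugs together: "When the start of a new treatment cycle with subcutaneous azacitidine is delayed for any reason, the infusion of durvalumab will also be delayed".

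On adverse events, Protocol 9.7 lists for tabulation "events leading to dose reduction/interruption/delay, events classified as CTCAE Version 4.03 Grade 3 or higher". SAP 12.1 has tables for reduction, for infusion interruption and for "TEAEs leading to dose interruption of azacitidine, durvalumab and azacitidine and/or durvalumab". It has none for delay, and SAP 15 does not mention the difference.

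**The concern.** A secondary objective (Protocol Table 1, SAP 3) compares tolerability between the combination and azacitidine alone. An obvious tolerability question is whether adding durvalumab makes azacitidine cycles run late. Protocol Appendix O records that the DMC later noted a potential for late events such as cytopenias, so the question has practical weight.

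The planned delay output cannot answer it. A delay summary defined on durvalumab has nothing to report for Arm B. In Arm A it mixes postponements caused by durvalumab with those in which durvalumab simply waited for a late azacitidine cycle. Read without that background, the table could suggest that delay belongs to the combination.

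**Working it through.** The plan states no figure on this point, so the check sets the sections side by side and adds one illustration.

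**Where a cycle postponed for cytopenia would appear**

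| Event | Azacitidine output | Durvalumab output |
|---|---|---|
| Postponed cycle, Arm A, both drugs ongoing | Interruption, if counted; cycle length; dose intensity; relative dose intensity | Interruption and delay, if counted |
| Postponed cycle, Arm A, durvalumab already stopped | Same as above | None |
| Postponed cycle, Arm B | Same as above | Not applicable |
| One missed mid-cycle injection, either arm | Interruption; dose intensity; relative dose intensity | None |

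Two things follow.

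1. In the azacitidine interruption row, a postponed cycle and a missed injection are indistinguishable. SAP 8.7 counts consecutive zeros as one interruption, so a long postponement weighs the same as one missed day, and no length is reported.
2. The entry *if counted* is unresolved. An interruption needs a zero-dose record and excludes zeros that the protocol requires. A cytopenia delay is protocol-directed. Under SAP 5.1.3 a late start simply lengthens the preceding cycle, because each cycle ends the day before the next one begins. The SAP does not say whether a zero record is created for the postponed days, or whether the exception removes it. Two programmers could produce different counts.

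**How far the indirect measures register delay**

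Assume six azacitidine cycles at full dose, with *D* days of total postponement spread over Cycles 2 to 6. Let *L* be total cycle length. From SAP 8.5 and 8.6:

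- actual intensity = 6 × 7 × 75 × BSA / *L*
- planned intensity = 7 × 75 × BSA / 28
- relative dose intensity (RDI) = 6 × 28 / *L* = 168 / *L*
- average cycle length = *L* / 6

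The SAP supports two ways of closing the last cycle. SAP 8.1 Table 3 runs it to Day 28, so *L* = 168 + *D*. SAP 5.1.3 runs it to last dose + 28 days, which is Day 35 after a Day 7 dose, so *L* = 175 + *D*.

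| *D* (days) | Mean cycle, last cycle 28 d | RDI | Mean cycle, last cycle 35 d | RDI |
|---|---|---|---|---|
| 0 | 28.0 | 100.0% | 29.2 | 96.0% |
| 14 | 30.3 | 92.3% | 31.5 | 88.9% |
| 28 | 32.7 | 85.7% | 33.8 | 82.8% |
| 42 | 35.0 | 80.0% | 36.2 | 77.4% |

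The example category in SAP 8.6 is at or below 85%. A full-dose subject reaches it when *L* = 168 / 0.85 = 197.6 days, that is *D* = 29.6 days under the first convention or 22.6 under the second. One 14-day postponement does not change the category under either.

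**The case against.** The strongest reply is that nothing is lost. SAP 8.7 makes delay a kind of interruption, and azacitidine interruptions are summarised in both arms, including those due to AE. A reader might infer that azacitidine delay has no table at all in Arm B. The SAP's own definition does not support that: what is missing is a separate delay summary. Nor is average cycle length the only trace, since dose intensity and RDI fall with delay in both arms and RDI is also reported by cycle.

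A reader might also infer that every azacitidine-driven delay in Arm A becomes a durvalumab delay. That goes too far. The zero-record condition applies to both drugs, and Protocol 3.2.2 lets subjects who stop durvalumab for drug-related toxicity continue azacitidine alone. Where durvalumab was held back it really was delayed, so such a row is not false; it just does not show the cause.

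Finally, Protocol 9.7 names reduction, interruption and delay in one combined item, which need not mean three tables. The action-taken examples in Protocol 10.2.5 do not include delay, and the dose-modification guidance is followed at the investigator's discretion.

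These points limit the finding but do not remove it. Pooling gives neither the number nor the length of delays, and the zero-dose exception leaves even the pooled count uncertain. The SAP evidently considers delay worth reporting apart from interruption, but does so only for the drug given in one arm.

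**Conclusion.** The point holds as a defect in descriptive safety reporting. SAP 8.7 explicitly excludes azacitidine from the delay summary, so the drug common to both arms has no like-for-like comparison of cycle delay. The only delay table is confined to Arm A and includes delays in which durvalumab followed a late azacitidine cycle.

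The effect on any reported rate cannot be sized. The documents give no frequency of cycle delay. The 71.4% in Protocol 1.3.1 is the frequency of hematological reactions and should not be read as a delay rate. What can be shown is how coarse the substitutes are: under the full-dose, six-cycle assumption, roughly 23 to 30 days of total delay are needed before the example RDI category registers it. RDI also mixes delay with reductions and omitted doses, and gives no reasons.

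No primary endpoint, hypothesis test or futility rule is touched. The change is worth making because the comparison serves a stated secondary objective and costs little.

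**What to change.** Reporting changes only; no dosing rule is involved.

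- **SAP 8.7, azacitidine:** summarise cycle delay by cohort in both arms from dosing dates, giving subjects with at least one delay, number and length of delays, and delays due to AE where the CRF records the reason.
- **SAP 8.7, durvalumab:** keep the delay summary but split it by whether the azacitidine cycle was also late.
- **SAP 8.7, definition:** state that toxicity-directed postponements count as delays, and say what the zero-dose exception is meant to exclude.
- **SAP 12.1:** add TEAEs leading to dose delay, in line with Protocol 9.7, or declare the departure in SAP 15.

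The cost is a few extra descriptive tables. Administration dates are already recorded (Protocol 7.2.1), so counts and lengths need only programming. Attribution to AEs is less certain: it depends on whether the CRF action-taken field separates delay from interruption, which the documents do not show and which should be checked first.

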9. CONCOMITANT MEDICATIONS/PROCEDURES AND SUBSEQUENT THERAPY

9.1. Concomitant Medications

Concomitant medications are defined as non-study medications that are started during the study treatment exposure period, or started before the start of the study treatment and ended or were ongoing during the study treatment exposure period. The study treatment exposure period is defined as the interval between the date of first administration of any study treatment and the later of 28 days after the last dose of azacitidine and 90 days after the last dose of durvalumab.

All concomitant treatments documented during the study treatment exposure period will be summarized in frequency tabulations by disease cohort for the ITT and Safety Populations. The ATC coding scheme of the WHO (September 2016 version, or higher) will be used to group medications into relevant categories for these tabulations.

Listings of concomitant medications by subject will be provided.

9.2. Concomitant Procedures

The CRF page records procedure, date, and indication. These procedures will be coded using MedDRA Version 19.0 or higher. A frequency summary of subjects by concomitant procedures summarized in frequency tabulations by SOC and preferred term by disease cohort for the ITT Population.

Concomitant procedures will be identified as procedures or surgeries that occurred after or on the date of first dose of durvalumab or azacitidine until 28 days after the last dose of subcutaneous azacitidine and 90 days after the last dose of durvalumab.

9.3. Subsequent Therapy

Whether subject had subsequent radiation therapy, cancer surgery, stem cell transplantation and hormonal anticancer therapy for this disease will be summarized with frequency counts and percentages. In addition, subsequent hormonal anticancer and systemic anticancer therapies will be summarized by ATC level 1 term, ATC 3 term and preferred name for the Safety Population. Details of subsequent therapies will be presented in subjects' data listings.

10. EFFICACY ANALYSIS

All efficacy analyses will be carried out on the ITT Population. Supportive efficacy analyses will also be performed using EE Population.

All efficacy endpoints will be summarized by disease cohort and treatment arm.

All confidence intervals (CIs) will be provided at a level of 95% and between-group comparisons will be provided as appropriate as described below.

10.1. Primary Efficacy Endpoint

The primary efficacy endpoint is the ORR and will be programmatically derived using the results/assessments generated by the central morphologic/cytogenetic and hematology laboratories. In case no central hematology results are available within +/- 8 days of bone marrow samples, local hematology results might be used if available. This analysis will be conducted after completion of the Stage 1 and Stage 2 portions of the study. A subject is considered evaluable for response if they have undergone at least one disease status assessment following treatment Cycle 6. Subjects who discontinue from the treatment phase before the first post baseline efficacy assessment (following treatment Cycle 3) will be replaced unless the subject had a documented progression of their disease or died and will be considered as non-responders. If one post baseline disease assessment is performed, this assessment would be considered for response.

The difference of the proportions for overall response between the azacitidine alone and combination therapy arms will be tested using a standard Wald asymptotic two-sided test with unpooled estimate of variance and presented along with corresponding two-sided 95% CIs.

The hypothesis tested will be:

$$H_0: d = 0$$

versus

$$H_a: d \neq 0,$$

Where $d = p_1 - p_2$ is difference in overall response rate in the combination therapy arm (p_1) versus the overall response rate in the monotherapy arm (p_2).

The test statistic is

$$z = \hat{d}/se(\hat{d})$$

Where, the standard error is computed from the sample proportions as

$$se(\hat{d}) = \sqrt{\frac{\hat{p}_1(1 - \hat{p}_1)}{n_1} + \frac{\hat{p}_2(1 - \hat{p}_2)}{n_2}}$$

Where \hat{p}_1 (respectively \hat{p}_2) is the estimated response rate in the combination therapy arm (respectively monotherapy arm) and is derived as the observed response rates in respective arms.

Myelodysplastic Syndromes Cohort

For the MDS cohort, the primary efficacy endpoint is the proportion of subjects achieving an overall response rate (defined as CR, PR, mCR, and/or HI) as determined using the International Working Group (IWG) 2006 response criteria for MDS ([Appendix 17.2](#)). The ORR will be summarized together with two-sided 95% CI. Subjects discontinued before 6-cycle treatment without achieving overall response will be counted as nonresponders.

The number and percentage of subjects who achieve each component of the overall response (CR, PR, mCR, HI-E, HI-P, HI-N) will be summarized together with associated two-sided 95% CI.

The best overall response per IWG 2006 response criteria will be summarized. The best overall response is defined as the best response prior to progressive disease and first subsequent therapy.

The below order will be considered for the definition of best response:

1. CR
2. PR
3. mCR
4. SD
5. PD
6. Disease transformation
7. Failure due to death
8. Not Evaluable/Missing

Acute Myeloid Leukemia Cohort

For the AML cohort, the primary efficacy endpoint is the proportion of subjects achieving an overall response rate (CR or CRi) based on modified IWG 2003 response criteria for AML ([Appendix 17.3](#)). The ORR will be summarized together with two-sided 95% CI. Subjects discontinued before 6-cycle treatment without achieving overall response will be counted as nonresponders.

The number and percentage of subjects who achieve CR, PR, CRi, HI-E, HI-P and HI-N will be summarized together with associated two-sided 95% CI

The best overall response per modified IWG response criteria will be summarized. The best overall response is defined as the best response prior to progressive disease and first subsequent therapy.

The below order will be considered for the definition of best response:

1. CR
2. CRi
3. CRc

4. PR
5. SD
6. PD
7. Treatment failure
8. Not Evaluable/Missing

